### **9.2.1 Measurement Methods**

Tumor diameter measurements: same as for primary endpoint

Progression-free survival: determined by medical record review and contacting participants or their outside medical providers as needed.

### **9.2.2 Measurement Time Points**

Initial response evaluation is performed by radiographic imaging at the same timepoints as for the primary endpoint. For repeat response evaluations on treatment, standard-of-care restaging imaging studies will be used. These, as well as determination of 12-month PFS, require follow-up at 12 months after initiation of treatment.

### **9.2.3 Response Review**

Response evaluation per RECIST v1.1 is reviewed by a designated radiologist, who may be the same person that performs the tumor diameter measurements.

## **10 STATISTICAL CONSIDERATIONS**

### **10.1 Statistical Design**

This is a pilot study to evaluate how well changes in tumor perfusion parameters, assessed by LEAD ultrasound 3 weeks after initiating treatment with TKI plus ICI, predict initial objective response, as determined by standard-of-care radiographic imaging 8-16 weeks after start of treatment. All secondary endpoints are exploratory and are intended for generating hypotheses that will require follow-up studies.

### **10.2 Descriptive Statistics and Exploratory Data Analysis**

We will characterize the study population by providing demographic and clinical characteristics. Categorical data will be presented as frequencies and percentages. For continuous data, mean, standard deviation, median, 25th and 75th percentiles will be presented. In addition, we will use graphical techniques to show the distribution of ultrasound parameters by the primary endpoint.

### **10.3 Primary Analysis**

#### **10.3.1 Analysis Population**

The population for primary analysis consists of all study participants who have completed the LEAD ultrasound exams at treatment 'baseline' and after 3 weeks of treatment, who received at least 4 weeks of TKI and at least one dose of ICI therapy, and for whom initial response can be evaluated per RECIST v1.1. If fewer than 20 of the 20 initially enrolled patients in arm 1 fulfill these criteria, additional patient may be enrolled

at the discretion of the Protocol Directors to have a complete dataset from 20 patients in arm 1 for primary analysis.

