## 5. STUDY PROCEDURES

### 5.1 Criteria for Removal from Study

Subjects are removed from active study participation (i.e., no further ultrasound exams), if

- they are non-compliant with study procedures;
- their treatment plan changes before the first ultrasound exam such that the new treatment plan does not qualify for this study;
- they start a different treatment during the active study participation period;
- for participants in arm 1, they receive less than 4 weeks of TKI treatment during the first 12 weeks after initiating TKI plus ICI therapy (i.e. minimum 4 of 12 weeks of TKI treatment and minimum one dose of ICI required for continued study participation);
- for participants in arm 2, they receive less than 4 weeks of systemic therapy during the first 12 weeks after initiating treatment. (For localized therapies, the minimum treatment requirements are determined by the Protocol Director.)

Subjects removed from active study participation with valid written consent are followed up per study protocol, so that data acquired by study procedures up to that time point can still be used for analysis.

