## 6. STUDY CALENDAR

	Pre-Study	Baseline (up to 28 days prior to initiating therapy) h	Standard-Of-Care Therapy			
			Week 3 (+/- 8 days) i	Week 6 (+/- 15 days) i	Week 12 (+/- 4 weeks) h	Before Study Completion j
Informed consent	X					
Doppler ultrasound exams a		X	X	X		
Standard-of-care imaging b	X				X	
Adverse event evaluation c				X		
Recording of age, race, ethnicity, sex, diagnosis, cancer stage, tumor histology, and drug treatment d,e				X (just once during any study timepoint)		
Documentation of lesions selected for ultrasound exam, scanners and modalities used, and imaged axis planes		X	X	X		
Quantification of tumor perfusion parameters f						X
Tumor diameter measurements g						X
Optional recording of medical history and other diagnoses, concurrent treatment and medication, additional treatment, follow-up, and survival data for future correlation studies e		X				X

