
a) Doppler ultrasound exams: power Doppler and LEAD ultrasound exams, performed during standard-of-care clinic visit or at research-only visit; if exam can be performed only with one of the two ultrasound scanners, only in one axis, or if one time point is missed entirely, subsequent exams may still be performed in full within their allowed time window.
 
b) Standard-of-care imaging: The baseline standard-of-care scan is generally within 6 weeks prior to initiating therapy, but may be greater than 6 weeks prior to therapy, if this is the scan that the treating physician chooses to use as reference for response evaluation. Preferably, this is a CT Chest-Abdomen-Pelvis (CAP) scan (with or without contrast), but it may also be an MRI or PET/CT or a combination of MRI and CT. At the discretion of the treating oncologist, the standard-of-care scan at week 12 may be performed outside of the +/- 4-week window.
 
c) Adverse event (AE) evaluation: Only AEs that are attributed to the study procedures are recorded and reported. During study procedures, study coordinator reminds patient to contact the clinical care team, if they experience any symptoms during the exam or afterwards. If the participant expresses to the coordinator that they have experienced symptoms during or after the exam, the coordinator will alert the clinical care team on the same day to contact the patient for AE evaluation and management. During baseline through week 12, patient will continue with standard-of-care provider visits at or outside of Stanford (generally, every 2-6 weeks, at the discretion of the treating clinical care team) including adverse event management. At week 12, a retrospective chart review will document any undisclosed study-related late adverse events and assure there are no ongoing study-related adverse events. If there is no adequate information in the medical record at week 12, patient will be contacted if needed to complete this documentation. Therefore, at minimum, there is one documented AE evaluation at week 12.
 
d) to be recorded once between baseline and study completion
 
e) may be obtained until study completion, even after a participant's death; patients or their outside medical providers may be contacted as needed to obtain the clinico-demographic data, if not available in the Stanford medical record.
 
f) to be quantified and recorded for all ultrasound exams from this study
 
g) RECIST measurements to be recorded for all imaging studies used for response evaluation (CT, MRI or PET/CT as described in footnote (b)). Performed at minimum at baseline and 12 weeks. RECIST measurements will also be recorded for other subsequent standard-of-care studies that the treating MD obtains at any interval to evaluate treatment response (until 12 months after initiating treatment or until end of the treatment that is being studied, whichever occurs first)
 
h) For combination treatments, initiation of therapy is typically defined by the day of starting treatment with the second drug, however another day (such as the start of treatment with the first drug) may be defined as start of treatment at the discretion of the Protocol Director; date considered start of treatment will be documented in the research procedure note in the electronic medical record.
 
i) 10 days is the minimum time period between week-3 and week-6 power Doppler ultrasound exams; similarly, 10 days is the minimum time period between week-3 and week-6 LEAD ultrasound exams; it is not required that power Doppler and LEAD ultrasound exams are performed on the same date.
 
j) Before end of study (3 years from date of study opening)
						

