## **9. MEASUREMENTS**

### **9.1 Primary Outcome Measures**

The primary endpoint is initial objective response per RECIST v1.1 assessed 8-16 weeks after start of treatment, using standard-of-care imaging. expressed as a number and proportion without dispersion.

Initial objective response (yes/no): defined as having either Complete Response (CR) or Partial Response (PR) per RECIST v1.1 at first on-treatment response evaluation 8-16 weeks after initiating treatment.

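### An otherwise qualifying arm 1 patient who dies before any on-treatment scan leaves the primary analysis and may be replaced; early progression without a week 8-16 evaluation is left unclear

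*Protocol*

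**What the plan says.** Section 10.3.1 of the protocol sets three conditions for the primary analysis. The first is completed LEAD exams at baseline and week 3. The second is a 4-week minimum of TKI treatment. The remaining requirements read "and at least one dose of ICI therapy, and for whom initial response can be evaluated per RECIST v1.1". Where some of the 20 arm 1 patients do not meet these conditions, others can be added "at the discretion of the Protocol Directors to have a complete dataset from 20 patients in arm 1 for primary analysis".

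Section 9.1 defines the endpoint as complete or partial response "per RECIST v1.1 at first on-treatment response evaluation 8-16 weeks after initiating treatment". Section 9.1.2 ties it to standard-of-care imaging at baseline and at week 12, plus or minus 4 weeks. No section says how a death before that imaging is classified.

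Three other provisions bear on early progression:

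- Section 5.1 takes a patient who starts a different treatment out of active participation, but follow-up continues "so that data acquired by study procedures up to that time point can still be used for analysis".
- Footnote b of the study calendar (section 6) says that, at the treating oncologist's discretion, "the standard-of-care scan at week 12 may be performed outside of the +/- 4-week window".
- Footnote g says "RECIST measurements will also be recorded for other subsequent standard-of-care studies that the treating MD obtains at any interval to evaluate treatment response". This recording stops at 12 months, or earlier if the studied treatment ends.

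On data capture, the calendar lists "Optional recording of medical history and other diagnoses, concurrent treatment and medication, additional treatment, follow-up, and survival data for future correlation studies". Section 9.2.1 says that progression-free survival is "determined by medical record review and contacting participants or their outside medical providers as needed".

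**The concern.** The evaluability condition acts after the week-3 predictor has been measured, and it depends on the outcome. A patient who dies before any on-treatment scan cannot have been a responder at weeks 8-16, so this route out of the analysis removes only non-responders. The rationale in section 2.4 names early detection of resistance as a purpose of the study, and these patients are among the clearest cases of treatment failure.

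The non-responder group is small to begin with: at the planning rate of section 10.5 it is 41% of 20, or 8.2 patients. Losing a few changes the response rate in the analysed set and the group against which the AUC is computed. Section 10.7 then uses an AUC of 0.7 as the minimum for designing a follow-up study.

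Replacement is an enrolment decision taken while the study runs. A later statistical analysis plan can redefine the population, but it cannot undo replacements already made or recover items that were never required.

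**Working it through.** **Step 1: who is affected, from the text.** Each patient below has both LEAD exams, at least 4 weeks of TKI and one ICI dose.

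| Course before the week 8-16 evaluation | Reading of 9.1 with 10.3.1 |
|---|---|
| Dies, no on-treatment scan | No RECIST evaluation exists: excluded, may be replaced |
| RECIST progression on a scan before week 8, no on-treatment evaluation in weeks 8-16 | Ambiguous: footnote g records the scan and section 5.1 keeps data acquired before removal, but 9.1 asks for an evaluation in weeks 8-16 |
| Scanned on treatment in weeks 8-16 | Classified as defined; no problem |

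A patient with less than 4 weeks of TKI is out under a separate criterion and is not part of this point. The period at issue therefore runs roughly from week 4 to the scan.

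**Step 2: the plan's own figures.** Section 10.5 gives 20 patients, 59% response, a true AUC of 0.7 and a margin of error of 0.14. Responders: 20 × 0.59 = 11.8. Non-responders: 20 × 0.41 = 8.2.

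The Hanley-McNeil standard error at A = 0.70 uses Q1 = A/(2 − A) = 0.538 and Q2 = 2A²/(1 + A) = 0.576:

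SE = √{[0.21 + 10.8 × (0.538 − 0.49) + 7.2 × (0.576 − 0.49)] / (11.8 × 8.2)} = 0.118 (computed with unrounded Q1 and Q2).

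The 95% margin is 1.96 × 0.118 = 0.23, so the stated 0.14 is not reproduced at 95%. That is a separate matter; the figures serve here only as a yardstick for sampling error.

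**Step 3: response rate.** Section 10.5 applies 59% to the 20 patients of the primary analysis, who by 10.3.1 are evaluable. So k early failures are added to those 20 as non-responders. The documents do not give k; 1 to 3 is an assumption.

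Rate = 11.8 / (20 + k). Share of all non-responders left out = k / (8.2 + k).

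**Step 4: AUC.** For a fixed score, the AUC is the average over non-responders of the probability that a responder outranks them. Let it be 0.70 for the evaluable non-responders and a for the added ones, with a assumed between 0.5 and 0.9:

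AUC = (8.2 × 0.70 + k × a) / (8.2 + k).

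| k | Response rate | Non-responders left out | AUC, a = 0.5 | AUC, a = 0.9 |
|---|---|---|---|---|
| 1 | 11.8/21 = 56% | 1/9.2 = 11% | 6.24/9.2 = 0.68 | 6.64/9.2 = 0.72 |
| 2 | 11.8/22 = 54% | 2/10.2 = 20% | 6.74/10.2 = 0.66 | 7.54/10.2 = 0.74 |
| 3 | 11.8/23 = 51% | 3/11.2 = 27% | 7.24/11.2 = 0.65 | 8.44/11.2 = 0.75 |

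The largest shift is 0.2 × k/(8.2 + k), that is 0.02, 0.04 or 0.05. At a = 0.7 there is none.

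**The case against.** The case for leaving the text alone has several parts.

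- *Requiring the reference standard is legitimate.* The pilot asks whether ultrasound predicts RECIST response, so restricting it to patients with a RECIST evaluation is coherent, and coding any-cause death as non-response adds some label noise. This stands as a cost, but not as a reason to replace patients whose non-response is known.
- *The certain group is small.* A patient must complete both exams, reach the exposure minimum and then die unscanned. No rate is given. This stands.
- *The effect is minor.* A shift of 0.02 to 0.05 lies below the stated margin of 0.14 and the recomputed standard error of 0.118, and section 10.5 says that no formal hypothesis is tested. This stands too, although a confidence interval does not reflect selection on the outcome.
- *Much is handled elsewhere.* RECIST progression is already recorded under footnote g, section 8.2 requires the secondary outcome measures in the eCRF, and section 10.4.1 keeps these patients available for secondary analyses. This stands. The optional calendar row concerns future correlation studies and does not show that progression goes unrecorded. Date of death is different: the section 9.2 definition of 12-month PFS names progression only.

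A reader might infer that every patient who progresses early or switches treatment is excluded. The documents do not support that: sections 5.1 and 6 allow an early progression scan to be read as an evaluable non-response. Nor do they support a claim that the AUC is inflated, because the direction depends on how the perfusion changes of the early failures compare with those of other non-responders.

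**Conclusion.** The point holds in a narrow form. By the stated rules, an otherwise qualifying arm 1 patient who dies before any on-treatment scan is excluded from the primary analysis and may be replaced. Early RECIST progression without a week 8-16 on-treatment evaluation is unresolved, which is not the same as excluded.

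Under the assumption of one to three such patients, the response rate falls from 59% to 56%, 54% or 51% when they are counted. An AUC of 0.70 moves to within 0.68-0.72, 0.66-0.74 or 0.65-0.75. These ranges rest on an assumed ranking probability of 0.5 to 0.9 and on a fixed score; the planned Lasso would be refitted with cross-validation, so the actual shift could differ.

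A reader might take the ranges to show that the follow-up decision is at risk. They do not: they straddle 0.7 because the calculation starts at 0.70. This is a point to consider. The reason to act is that the rule selects on the outcome and is cheap to correct, not that a large bias has been shown.

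**What to change.** Keep the LEAD-exam and exposure criteria of section 10.3.1, and keep the section 9.1 definition unchanged for every patient who has an on-treatment evaluation in weeks 8-16. A patient with progression on an early scan who is later evaluated on treatment in the window is then still classified by that evaluation.

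Add to both sections: an otherwise qualifying arm 1 patient with no on-treatment evaluation in weeks 8-16, because of death or because of RECIST progression documented on an earlier scan, is included as a non-responder and is not replaced. Patients with no outcome for other reasons stay out, may be replaced, and are reported with reasons. Report the present RECIST-evaluable population as a sensitivity analysis.

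Make two eCRF items required: the date of a death before the first evaluation, and the reason for a missing evaluation.

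The cost is a short addition to two sections and two data items, obtainable through the record review and provider contact already foreseen in sections 6 and 9.2.1. The downside is that a death from any cause counts as non-response and the reported response rate may fall slightly.

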### 10.3.2 Analysis Plan

To address our primary objective, we will conduct a Least absolute shrinkage and selection operator (Lasso) regression as our primary analysis. Specifically, our outcome, initial objective response, will be regressed on the change in each of the LEAD ultrasound tumor perfusion parameters after 3 weeks of treatment and relevant demographic and clinical characteristics. The measurement of LEAD ultrasound tumor perfusion parameters and the definition of their change are described in more detail below. We will not use selection techniques to choose variables. Rather, we will include all factors in our model jointly. We will evaluate the predictive ability of our model using area under the curve (AUC) and calculate a 95% confidence interval for the AUC. Since our sample size is too small to allow for separate training and testing datasets, we will utilize cross-validation techniques for evaluating predictive performance.

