## 1. OBJECTIVES

### 1.1 Primary Objective

Our primary objective is to assess whether in arm 1, changes in quantitative tumor perfusion parameters 3 weeks after start of treatment of metastatic renal cell carcinoma (mRCC) patients with tyrosine kinase inhibitor (TKI) plus immune checkpoint inhibitor (ICI), as measured by LEAD ultrasound, can predict initial objective response to therapy at 12 weeks after start of treatment defined by current standard-of-care Response Evaluation Criteria In Solid Tumors (RECIST v1.1).

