### 10.4.2 Analysis Plan

To address our secondary objective, i.e., evaluating if there is an optimal ultrasound modality to predict initial objective response in arm 1, we will utilize the same analysis approach as outlined above for the primary analysis. Here, we will use change in tumor perfusion parameters at **6 weeks** as our independent variables and conduct two regression analyses: (1) using power Doppler measurements and (2) using LEAD ultrasound measurements. AUCs between the two models will be compared using the nonparametric approach of DeLong for correlated AUC curves. In addition, we will compare AUCs between these models to the predictive model for the primary analysis.

To assess if there is an optimal time point for predicting initial objective response in arm 1, we will conduct Lasso regression models using tumor perfusion parameters for each time point (treatment 'baseline', 3 weeks, 6 weeks) separately for each imaging modality using a similar approach as outlined above. Given the exploratory nature of these analyses, we will not adjust for multiple testing.

For each arm, we will conduct correlation analysis for change in perfusion parameters at 3 and 6 weeks and initial relative change in tumor burden (overall and per-lesion), initial overall response, best overall response, and PFS until 12 months after initiating treatment by calculating either the Pearson r or Spearman rank correlation, as appropriate. PFS is estimated using the Kaplan-Meier method and the Kaplan-Meier curves will be presented.

Selection of lesions for ultrasound exams:

The up to 5 lesions that were selected for ultrasound studies for the primary analysis are re-assessed 6 weeks (+/- 15 days) after start of treatment and each lesion is assessed with both LEAD and power Doppler ultrasound at all 3 time points (treatment 'baseline', 3 weeks, and 6 weeks after initiating treatment).

Quantification and change of tumor perfusion parameters: defined in the same way as for the primary analysis for both power Doppler and LEAD ultrasound.

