## **10.7 Criteria for future studies**

An AUC of at least 0.7 will be the minimum needed to design a follow-up study and the predictive model that yields the best AUC will be selected for future studies. If different predictive models give equivalent AUCs, we will consider additional analyses (for example, random forests or Classification and Regression Tree [CART]) to evaluate these models to determine if a specific model can be selected for further studies.

If any predictive model from this pilot study has an AUC of at least 0.7, the next step will be to conduct a larger follow-up study in an independent cohort to validate the predictive model and determine its AUC with a smaller margin of error. The sample size and operating characteristics of the follow-up study will be determined based on findings from this pilot study and other data available at the time of designing the follow-up study. If the larger follow-up study is also deemed a success (AUC at least 0.7), to determine if tumor perfusion measurements by ultrasound are suitable for implementation, an adequately powered randomized clinical trial will be required to

Early Therapeutic Monitoring of Response to Therapy with Serial Ultrasound in Metastatic Renal Cell Carcinoma

test if an early therapy switch based on ultrasound imaging improves outcomes, compared to current standard of care.

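### The primary AUC mixes LEAD changes with clinical covariates, no AUC isolates either, and the 0.7 criterion can be met without LEAD

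*Protocol*

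**What the plan says.** The question concerns LEAD only. Section 1.1 asks whether "changes in quantitative tumor perfusion parameters 3 weeks after start of treatment", measured by LEAD, can predict response at 12 weeks. Section 10.1 describes the aim of the pilot as finding out "how well changes in tumor perfusion parameters, assessed by LEAD ultrasound 3 weeks after initiating treatment with TKI plus ICI, predict initial objective response". Neither mentions clinical predictors.

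The primary analysis (section 10.3.2) is a single Lasso. Response is "regressed on the change in each of the LEAD ultrasound tumor perfusion parameters after 3 weeks of treatment and relevant demographic and clinical characteristics", with all factors entered together. Performance is the AUC of that model with a 95% confidence interval, evaluated by cross-validation.

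For the 6-week comparison of modalities, section 10.4.2 states that "we will utilize the same analysis approach as outlined above for the primary analysis", and adds that "we will compare AUCs between these models to the predictive model for the primary analysis". The single-time-point models follow a similar approach, with no word on covariates.

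Section 10.7 begins its follow-up rule with "If any predictive model from this pilot study has an AUC of at least 0.7"; a larger study in an independent cohort is then the next step. The same section says that "the predictive model that yields the best AUC will be selected for future studies".

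**The concern.** The objective is about an imaging marker, but the primary measure belongs to a model that contains the marker and other predictors. A Lasso can shrink every LEAD coefficient to zero, and the fitted model would still have an AUC that counts towards the 0.7 criterion. An AUC of, say, 0.75 would not show whether it came from LEAD, from the covariates or from both.

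The go decision is at stake. Section 10.7 judges the follow-up study by the same AUC threshold, so a clinical factor that truly predicts response would be expected to replicate there too. Validation of the joint model would then not reveal that ultrasound contributed nothing. The step after that is a randomized trial of switching therapy early on the basis of ultrasound, where attribution to ultrasound is essential.

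**Working it through.** **1. What each planned AUC can answer**

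| Planned model | Section | Models | 3-week LEAD changes only? | Clinical only? |
|---|---|---|---|---|
| 3-week LEAD changes + covariates | 10.3.2 | 1 | No | No |
| 6-week changes, power Doppler and LEAD | 10.4.2 | 2 | No | No |
| Values at baseline, 3 and 6 weeks, two modalities | 10.4.2 | 3 × 2 = 6 | No (levels, not changes) | No |

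None of the nine models isolates the 3-week LEAD changes or the clinical factors. If covariates enter the eight secondary models, no perfusion-only AUC exists anywhere. If they do not, the planned comparison of the 6-week models with the primary model sets models without covariates against one with them.

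**2. Inputs for the size of the problem**

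- From section 10.5: n = 20 and 59% responders. 0.59 × 20 = 11.8, taken as 12 responders and 8 non-responders, or 12 × 8 = 96 pairs. An AUC of at least 0.7 needs 0.7 × 96 = 67.2, so 68 concordant pairs.
- Assumed, because the protocol gives none of it: three normal covariates, at most one informative; three LEAD changes with mutual correlation 0.7; 5-fold stratified cross-validation with pooled out-of-fold scores and the same folds for every model. A covariate with true AUC A is shifted by d = √2 · Φ⁻¹(A); for A = 0.70, d = 1.414 × 0.524 = 0.74 SD.
- Each cell gives the result for a fixed penalty of 0.05 (2000 trials) / a penalty tuned by nested cross-validation (1000 trials).

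The plan's own figure in section 10.5, a margin of error of 0.14, is not used. It does not reproduce as a 95% margin (Hanley-McNeil SE 0.119; 1.96 × 0.119 ≈ 0.23), but that is a separate matter.

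**3. LEAD as pure noise**

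| True AUC of one covariate | Joint ≥ 0.7 | Clinical-only ≥ 0.7 | Joint ≥ 0.7 and no better than clinical-only |
|---|---|---|---|
| 0.50 | 10.1% / 4.5% | 8.4% / 3.6% | 3.5% / 1.4% |
| 0.60 | 12.4% / 6.5% | 12.0% / 6.6% | 5.6% / 2.1% |
| 0.70 | 23.6% / 15.3% | 26.8% / 17.8% | 13.3% / 7.8% |
| 0.77 | 39.2% / 29.0% | 43.1% / 32.9% | 24.5% / 18.2% |
| 0.86 | 68.2% / 59.1% | 75.6% / 65.4% | 49.8% / 38.7% |

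LEAD-only reaches 0.7 in 7.2% / 4.8%. Varying the fixed penalty from 0.02 to 0.10 moves the joint figure only between 22.9% and 23.5% at covariate AUC 0.70, and between 65.6% and 72.5% at 0.86.

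A separate simulation with another penalty and 4 folds (1000 runs) gave joint AUC ≥ 0.7 in 11%, 23% and 68% of runs at covariate AUC 0.50, 0.70 and 0.85, with LEAD-only at 7-10% throughout. The joint AUC follows the clinical factor.

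**4. Is a LEAD-only AUC enough?**

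Suppose LEAD correlates 0.6 with the informative covariate and adds nothing beyond it. LEAD-only then reaches 0.7 in 17.5% / 12.1%, 26.0% / 18.9% and 48.6% / 38.6% of trials at covariate AUC 0.70, 0.77 and 0.86, while the mean gain of joint over clinical-only is about zero (between -0.02 and 0.00). LEAD-only shows prediction; only the comparison with clinical-only shows added value.

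**5. When LEAD does predict**

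Each LEAD parameter has true AUC 0.70, independent of the covariates.

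| Covariates | LEAD-only ≥ 0.7 | Joint ≥ 0.7 | Mean gain over clinical-only |
|---|---|---|---|
| All noise | 34.2% / 26.1% | 29.5% / 19.5% | 0.153 / 0.078 |
| One with AUC 0.70 | 34.2% / 26.1% | 41.5% / 31.2% | 0.093 / 0.059 |

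Uninformative covariates can also hide a real LEAD signal, so the mixture works in both directions.

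**The case against.** The strongest reply has four parts.

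- *Added value over clinical factors is not in the objective.* True: sections 1.1 and 10.1 ask only whether LEAD predicts. Taken literally, the objective requires the LEAD-only AUC alone. The clinical-only reference is needed because the protocol itself chose a joint model, whose AUC cannot be read without it, and because of step 4 above.
- *LEAD is already examined separately.* Section 10.2 says "we will use graphical techniques to show the distribution of ultrasound parameters by the primary endpoint", and section 10.4.2 correlates 3-week changes with initial response. For 12 against 8, Spearman's rho equals 1.699 × (AUC - 0.5), so rho 0.34 corresponds to AUC 0.7 for a single parameter. This is useful, but it treats one parameter at a time, Spearman is only one of two options, and neither analysis feeds the 0.7 rule.
- *The criterion is only a minimum, and validation follows.* Section 10.7 does first call 0.7 the minimum needed, but its later sentence makes reaching it the trigger for the next study. Every planned model contains ultrasound, so no clinical-only model can be chosen as such; a joint model driven by covariates can.
- *The large percentages need strong covariates.* This stands. Section 8.2 requires only age, race, ethnicity, sex, diagnosis, stage, histology and drug treatment, and nothing in the protocol says how well these predict.

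The covariate list, and whether covariates enter the section 10.4.2 models, are details an SAP could settle. The joint model, its AUC as the measure, and the 0.7 rule are fixed in the protocol.

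**Conclusion.** The concern holds. Followed exactly, the plan produces a primary AUC that cannot be attributed to LEAD and a go criterion that does not require LEAD to contribute. That the criterion can be met without LEAD follows from the text alone; how often depends on assumed covariate strength, penalty and folds. With LEAD as noise, the main simulation gives 5-12% of trials at a covariate AUC up to 0.60, 15-24% at 0.70 and 59-68% at 0.86. These figures are illustrations, not forecasts for this trial.

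The consequence is confined to the pilot's go decision. Section 10.5 tests no formal hypothesis, and section 10.7 requires an independent cohort next. The change is well worth making, but the point does not invalidate the study.

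**What to change.** - **Section 10.3.2:** report cross-validated AUCs with 95% confidence intervals, in the same folds, for (a) the three 3-week LEAD changes only, (b) the clinical factors only and (c) the joint model. Report the gain of (c) over (b) as an estimate, not a test. State that (a) answers whether LEAD predicts response and that the gain shows whether it adds to clinical factors.
- **Section 10.7:** state that a joint AUC of at least 0.7 is not sufficient by itself and that the go decision is read together with (a) and the gain.
- **Section 10.4.2:** state whether covariates enter the modality and time-point models. If they do, report perfusion-only AUCs there too; if not, compare the 6-week models with (a) rather than with the joint model.

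**Cost:** protocol wording, two extra fits for the primary analysis and up to eight for the secondary ones, all on data already planned. The LEAD-only AUC may come out below the joint AUC. The gain is imprecise at n = 20: its SD across simulated trials was 0.06-0.14 with LEAD as noise and about 0.17 with LEAD and one covariate both informative (0.15-0.19 in a repeat with informative LEAD). A hard gate is not advised: requiring joint and LEAD-only AUCs both at least 0.7 and a positive gain would pass only 17-24% of trials when LEAD and one covariate each have a true AUC of 0.70.
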